AIMer	A-to-I editing oligonucleotide
ALT	alanine transaminase
aPTT	activated partial thromboplastin time
AST	aspartate transaminase
AUC; AUC _{0-24hr} ; AUC _{0-48hr} ; AUC _{last} ; AUC _{inf} ; AUC _{ext} ; AUC _{tau}	area under the curve; AUC from time 0 to 24 hours; AUC from time 0 to 48 hours; AUC from time 0 to last measurable concentration; AUC from time 0 to infinity, AUC extrapolated to infinity; AUC over a dosing interval
BMI	body mass index
bpm	beats per minute
BUN	blood urea nitrogen
BSA	body surface area
CBC	complete blood count
CFR	Code of Federal Regulations
CIOMS	Council for International Organizations of Medical Sciences
CL	clearance
C _{max}	maximum (peak) concentration of drug
COPD	chronic obstructive pulmonary disease
CRO	contract research organization
CRP	C-reactive protein
CRU	clinical research unit
CSR	clinical study report
CTCAE	Common Terminology Criteria for Adverse Events
cum Ae%	cumulative Ae%
CV%	percent coefficient of variation
DEC	Dose Escalation Committee
DMC	Data Monitoring Committee
EC	ethics committee

Abbreviation or Acronym	Definition
ECG	electrocardiogram
eCRF	electronic case report form
EDC	electronic data capture
eGFR	estimated glomerular filtration rate
EMA	European Medicines Evaluation Agency
ET	early termination
FIH	first-in-human
FSH	follicle stimulating hormone
GalNAc	N-acetylgalactosamine
GCP	Good Clinical Practice
GLDH	glutamate dehydrogenase
HBsAg	hepatitis B surface antigen
hCG	human chorionic gonadotropin
HED	human equivalent dose
HIV	human immunodeficiency virus
HRT	hormone replacement therapy
HV	healthy volunteer
IB	Investigator's Brochure
ICF	informed consent form
ICH	International Council for Harmonisation
INR	international normalized ratio
IRB	institutional review board
IUD	intrauterine device
IUS	intrauterine hormone-releasing system
M-AAT	M allele (wild type) version of AAT protein
MCH	mean corpuscular hemoglobin
MCHC	mean corpuscular hemoglobin concentration
MCV	mean corpuscular volume
MedDRA	Medical Dictionary for Regulatory Activities
mRNA	messenger ribonucleic acid
MTD	maximum tolerated dose level
NCI	National Cancer Institute
CC	

Abbreviation or Acronym	Definition
NOAEL	no observed adverse effect level
PD	pharmacodynamic
PK	pharmacokinetic
PT	preferred term
Q2W	every other week
QTcF	QT interval corrected using Fridericia's formula
RBC	red blood cell
RNA	ribonucleic acid
SAD	single ascending dose
SAE	serious adverse event
SAR	serious adverse reaction
SC	subcutaneous
SD	standard deviation
SERPINA1	Serpin Family A Member 1
SoA	schedule of assessments
SOC	system organ class
SpO ₂	percentage oxygen saturation in the blood
SUSAR	suspected unexpected serious adverse reaction
t _½	terminal elimination half-life
TEAE	treatment emergent adverse event
t _{max}	time to C _{max}
ULN	upper limit of normal
USFDA	United States Food and Drug Administration
Vd	volume of distribution
WBC	white blood cell
WOCBP	women of childbearing potential
Z-AAT	Z allele (mutant) version of AAT protein

1 PROTOCOL SUMMARY

1.1 Protocol Synopsis

Sponsor: Wave Life Sciences UK Limited	Investigational Product: WVE-006	Developmental Phase: Phase 1	IRAS ID Number: 1008635
Protocol Title: A Phase 1, Randomized, Double-blind, Placebo-controlled, Safety, Tolerability, and Pharmacokinetic Study of Single Ascending Doses and Multiple Doses of WVE-006 in Healthy Participants			
Protocol Number: WVE-006-001			
Brief Title: A Phase 1, Randomized, Double-blind, Placebo-controlled, Single Ascending Dose and Multiple-Dose Study of WVE-006 in Healthy Participants			
Pediatric Investigation Plan Number: Not applicable			
Rationale: 
Alpha-1 antitrypsin (AAT) is an acute phase protein predominantly produced by hepatocytes. Serum AAT protects the lung against proteolytic enzymes such as neutrophil elastase. Alpha-1 antitrypsin deficiency (AATD) is caused by mutations in the Serpin Family A Member 1 (SERPINA1) gene which follow an autosomal, codominant recessive inheritance pattern with a codominant genetic trait for AAT production. 95% of severe AATD cases are due to homozygous substitution of a single amino acid, Glu342Lys (protein inhibitor [PI]*ZZ). This produces a mutant (Z) misfolded and poorly secreted AAT protein (Z-AAT). The retention of misfolded Z-AAT protein in the liver causes proteotoxic stress leading to progressive gain of function liver disease from fibrosis to cirrhosis to risk of hepatocellular carcinoma. In contrast, the deficiency of AAT in serum leads to loss of function pulmonary disease which is manifested as chronic obstructive pulmonary disease (COPD), mostly emphysema and bronchiectasis.
 
WVE-006 is an oligonucleotide that was designed to specifically edit the SERPINA1-Z messenger ribonucleic acid (mRNA) back to wildtype (M). Editing of the SERPINA1-Z mRNA back to wild type is expected to increase the concentration of M-AAT protein in the serum and decrease the accumulation of Z-AAT in the liver, thus addressing both the lung and liver disease manifestations associated with AATD.
 
WVE-006 is not expected to have pharmacological activity in healthy volunteers (HV) as they do not have the mutation.
			
Study Center(s): Up to 4 clinical research units			
Objectives and Endpoints:			
Objectives		Endpoints	
Primary			

 To evaluate the safety and tolerability of WVE-006 		
 Incidence of treatment emergent adverse events (TEAEs), related TEAE, severe TEAE, serious TEAE Changes in safety assessment parameters (e.g., physical exam, vital signs, clinical laboratory results, electrocardiograms (ECGs) [including any changes to QTcF]) 	

Sponsor: Wave Life Sciences UK Limited	Investigational Product: WVE-006	Developmental Phase: Phase 1	IRAS ID Number: 1008635
		
Tolerability based on incidence of discontinuation due to TEAEs	
Secondary			

To evaluate the pharmacokinetics (PK) of WVE-006 after a single dose in healthy participantsTo evaluate the PK of WVE-006 after multiple doses in healthy participants		
PK parameters of WVE-006 in plasma, including AUC_{inf}, AUC_{0-24h}, AUC_{0-48h}, AUC_{last}, C_{max}, t_{max}PK parameters of WVE-006 in plasma following first and last doses, including AUC_{tau}, AUC_{0-24h}, AUC_{0-48h}, AUC_{last}, C_{max}, t_{max}	
Exploratory			

To evaluate urine excretion of WVE-006		
Amount excreted (Ae), Ae% and cumulative Ae% (cum Ae%) for parent drug, as well as potential metabolites in urine	

Overall Design:

The purpose of this first-in human (FIH), double-blind, randomized, placebo-controlled, single ascending dose (SAD) and multiple-dose Phase 1 study is to assess the safety, tolerability, and PK of WVE-006 compared to placebo in healthy participants following a single dose (Period 1) and multidose (Period 2) of WVE-006.

Following screening of up to 28 days, eligible participants will be enrolled into Period 1 SAD. Following evaluation of the highest single dose cohort, 8 new participants will be enrolled into Period 2 for administration of 3 doses every other week (Q2W) at the selected dose level from Period 1. In both Periods 1 and 2, participants will be evaluated for safety and tolerability through Day 85 following their last dose of WVE-006 or placebo, as well as for various PK parameters.

Period 1

Period 1 will evaluate single ascending doses of WVE-006 in up to five cohorts of up to 8 healthy participants each. An additional cohort (Cohort 6) may be included to evaluate concentration-QTc. Each cohort will include up to 6 WVE-006-treated and up to 2 placebo-treated participants (3:1 active:placebo). Participants will receive a single subcutaneous (SC) dose of WVE-006 or placebo on Day 1.

The starting dose and dose escalation are designed based on the following considerations:

CCI

The Dose Escalation Committee (DEC) and the Data Monitoring Committee (DMC) will review available safety and PK data through Day 8 for each dose cohort in combination with all available, previously accumulated safety data, as well as available PK data from participants enrolled in the study to date, to recommend subsequent dose escalation.

A sentinel strategy will be employed for the first 2 participants (1 active:1 placebo) of every new dose level during the SAD portion of the study. The sentinel participants will be dosed and monitored in the clinic for a minimum of 48 hours to identify any potential acute safety events. If neither of these sentinel participants experiences stopping criteria and if there are no other safety concerns during this 48-hour period, the remaining 6 participants will be randomized in a blinded fashion to active study drug (n=5) or placebo (n=1) and may be dosed on the same day. These participants will be observed in clinic for 48 hours after administration of study drug. Participants will attend weekly clinic visits on Weeks 0 through 12 to be followed for safety, tolerability, and PK assessments through Day 85 per schedule of assessments (SoA).

Period 2

In Period 2, a single cohort of up to 8 healthy participants including up to 6 WVE-006 and up to 2 placebo treated participants (3:1 active:placebo) will participate in a multidose cohort of WVE-006. The DEC and DMC will review available safety and PK data from Period 1 to select the maximum tolerated dose level (MTD) with an acceptable PK profile. The MTD is defined as the dose below a dose level where any of the dose escalation stopping rules were met. If the MTD is not achieved in Period 1 (i.e., no dose escalation stopping rules were met and all doses were well tolerated), then the highest dose reached in Period 1 will likely be selected for Period 2. The DEC and DMC may select a lower dose based on all available information. At least 4 weeks of safety data for the proposed dose and all available data from the study must be available from Period 1 in order to inform the DEC and DMC Period 2 dose selection. A sentinel strategy will be employed for the first 2 participants

Sponsor:	Investigational Product:	Developmental Phase:	IRAS ID Number:
Wave Life Sciences UK Limited	WVE-006	Phase 1	1008635

(1 active:1 placebo) during the multiple dose portion of the study. The sentinel participants will be dosed and monitored in the clinic for a minimum of 48 hours to identify any potential acute safety events. If neither of these sentinel participants experiences stopping criteria and if there are no other safety concerns during this 48-hour period, the remaining 6 participants will be randomized in a blinded fashion to active study drug (n=5) or placebo (n=1) and may be dosed on the same day. WVE-006 or placebo will be administered every other week (Q2W) over 4 weeks (total of 3 doses; Weeks 0, 2, and 4). Following the first dose (Week 0) and last dose (Week 4), all participants will stay in the clinic for two nights for PK assessments. Following the second dose (Week 2), all participants will be observed for safety evaluation in the clinic for at least 4 hours post-study drug administration or per local SOP (whichever is longer). All participants will attend weekly follow-up clinic visits for safety, tolerability, and PK assessments through Week 12 followed by visits every 4 weeks through week 16 or early termination visit.

Dose Escalation Stopping Criteria (Period 1):

Dose escalation will be paused until further evaluation by the DMC if any of the following criteria are met. If it is confirmed that a stopping criterion was met, no further dosing will take place until after submission and approval of a substantial amendment if the DMC recommends the trial can continue.

- One or more participants experiencing at least possibly related Common Terminology Criteria for Adverse Events (CTCAE) Grade ≥ 3 TEAE or CTCAE grade ≥ 3 laboratory abnormality in a single cohort.
 - All grade 3 toxicities for vital signs must be confirmed with a repeat measurement obtained within 1 hour.
 - All grade 3 toxicities for laboratory parameters must be confirmed with a repeat measurement obtained within 24 hours.
- Two or more participants experiencing at least possibly related CTCAE grade ≥ 2 TEAEs or CTCAE Grade ≥ 2 laboratory abnormalities in a single cohort.
 - All grade 2 toxicities for vital signs must be confirmed with a repeat measurement obtained within 1 hour.
 - All grade 2 toxicities for laboratory parameters must be confirmed with a repeat measurement obtained within 24 hours.
- One or more participants experiencing any at least possibly related SAE in a single cohort.

Period 2 Individual Stopping Criteria:

Dosing will be paused or discontinued (per Investigator judgment) for an individual participant at any time in the study if:

- Participant experiences any severe or serious adverse event considered at least possibly related to study drug.
- Participant experiences, in the Investigator's opinion, clinically significant hypersensitivity to WVE-006 (or placebo) administration.
- Participant has any medical condition that is judged by the Investigator to jeopardize the participant's safety if he or she continues to receive the study drug.

On discontinuation of treatment, participants will be encouraged to continue follow-up for safety per protocol. Per Investigator judgment with consultation with the Sponsor, the participant may be allowed to resume participation in the study if/when the event has resolved.

Sponsor: Wave Life Sciences UK Limited	Investigational Product: WVE-006	Developmental Phase: Phase 1	IRAS ID Number: 1008635

Number of Participants (Planned): Up to 48 participants are planned to be enrolled; up to 40 participants in Period 1 (8 per each of the up to five planned SAD cohorts) and up to 8 new participants in the multidose Period 2.
 
Should the DEC and DMC recommend to include an optional SAD cohort, an additional 8 participants will be enrolled for a total of up to 56 participants. Fewer than 48 participants may be enrolled if the DEC and DMC decide fewer cohorts are needed.
			

Study Arms and Duration:
 
Study arms in both Period 1 and Period 2 are up to 6 WVE-006 and up to 2 placebo treated participants (3:1 active:placebo) in each of the planned cohorts.
 
Period 1 SAD: duration for each participant is expected to be up to 16 weeks: Screening of up to 28 days, followed by a single dose administration on Day 1, followed by safety, tolerability, and PK assessment through Day 85.
 
Period 2 Multidose: duration for each participant is expected to be up to 20 weeks: Screening of up to 28 days, followed by 3 dose administrations on Weeks 0, 2, and 4, followed by safety, tolerability, and PK assessment through Day 113 Visit (i.e., Day 85 following last dose administration).
			

Eligibility Criteria:
 
Participants must meet all inclusion criteria and none of the exclusion criteria. For eligibility purposes, abnormal laboratory or vital signs or ECG results may be repeated once during the Screening period or Day -1 (as applicable) for confirmation if an abnormal result is observed at the initial assessment.
 
Inclusion criteria
 
 Participant is capable of understanding and be willing to provide written informed consent prior to any study-related procedures. Participant is capable of understanding and adhering to all the requirements, procedures, instructions, and restrictions required by the protocol including scheduled visits, drug administration plan, laboratory tests, and likely to complete the study as planned. Healthy as determined by the Investigator, based on a medical evaluation, including medical history, concomitant medications, full physical examination, vital signs, laboratory tests, and ECGs at Screening and Day -1. Per Investigator's judgement, there should be no evidence of cardiovascular, pulmonary, endocrine, hepatic, biliary, gastrointestinal, neurological, hematological, immunological, metabolic, skeletal, renal, psychiatric disorders, or cancer within the past 5 years prior to Screening visit (except localized or in situ cancer of the skin). Clinical abnormality or laboratory parameter(s) outside normal range must not be clinically significant or unlikely to introduce additional risk to the participant nor interfere with the study procedures nor the interpretation of any of the study assessments. Male or female healthy participants 18-65 years of age at Screening Visit. Participant has a body mass index (BMI) between 18 to 32 kg/m² inclusive at Screening and Day -1 Visits. Genetic testing confirming PI*MM. Participant has been a non-smoker for at least 1 year prior to screening and agrees to abstain from tobacco and nicotine containing products for the duration of the study. Women of childbearing potential (WOCBP) must be: 
 Non-pregnant as determined by a negative serum pregnancy test at Screening and negative highly sensitive urine pregnancy test on Day -1. Non lactating. 			

[figure not shown]
Sponsor:	Investigational Product:	Developmental Phase:	IRAS ID Number:
Wave Life Sciences UK Limited	WVE-006	Phase 1	1008635


c) Agree to use a highly-effective method of contraception (as defined in Section 10.4) from CCI prior to Day 1 and for at least CCI following last study drug administration. Exception: Women exclusively engaging in same-sex sexual activities are not required to meet this criterion.
 
d) Must be willing to forgo ova (egg) donation for at least CCI following the last study drug administration.
 
9. Women of non-childbearing potential are defined as meeting at least 1 of the following criteria:
 
a) At least 12 months post-menopausal and has an FSH >40 mIU/mL.
 
b) Surgically sterile, defined as having a documented bilateral oophorectomy, or hysterectomy.
 
10. Male participants must be willing to follow contraceptive requirements (as defined in Section 10.4) and should not impregnate anyone while they are in the study and for at least CCI following the last dose of study drug. In addition, participant must be willing to forgo sperm donation for at least CCI following the last dose of study drug. Men exclusively engaging in same-sex sexual activities are not required to meet this criterion.
 
Exclusion criteria
 
1) Participant has a history of multiple drug allergies or of allergic reaction to an oligonucleotide or to N-acetylgalactosamine (GalNAc).
 
2) Participant has a history of intolerance or any medical condition that might interfere with SC injection(s).
 
3) History or signs or symptoms of severe (bacterial, viral, parasitic, or fungal) infection within 4 weeks prior to Screening or Day -1 Visits.
 
4) History or signs or symptoms of an acute illness (including COVID-19) within 10 days prior to dosing on Day 1 Visit. Exception: mild seasonal allergies.
 
5) Positive COVID-19 test, if applicable per site SOP, at Screening and Day -1 Visit.
 
6) Participant received a COVID-19 or any other vaccine within 14 days before dosing on Day 1 Visit or is scheduled for vaccination anytime during the study.
 
7) Participant has total bilirubin > upper limit of normal (ULN) though participants with documented Gilbert's syndrome with normal conjugated bilirubin are eligible; aspartate transaminase (AST) and/or alanine transaminase (ALT) >ULN at Screening and Day -1.
 
8) Participant has estimated glomerular filtration rate (eGFR) ≤ 60 ml/min/1.73mm² (calculated by the Cockcroft-Gault formula) at Screening and Day -1.
 
9) Participant has a positive serology for hepatitis B or hepatitis C at Screening; participants with positive hepatitis B serology may be enrolled if there is evidence the participant received HBV immunization.
 
10) Participant is known to be positive for human immunodeficiency virus (HIV) and/or positive serology for HIV 1/2 where testing is permitted per local regulations.
 
11) Participant has a history of regular alcohol consumption exceeding 14 standard drinks/week. 1 standard drink is equivalent to 14g ethanol or 5 US fluid ounces (fl oz) (150 mL) of wine (approximately 12% alcohol by volume), 12 fl oz (360 mL) of beer (approximately 5% alcohol by volume), or 1.5 fl oz (45 mL) of hard liquor (approximately 40% alcohol by volume), within 1 year prior to the Screening Visit.
 
12) Participant has a history of caffeine consumption exceeding 8 cups of coffee/day (1 cup = 8 fl oz [240mL]) within 14 days prior to first study dose, or consumption of any caffeine or chocolate containing products for 3 days prior to clinical research unit admission. Caffeine-containing food and/or beverages (e.g., tea, cola) should be considered equivalent to coffee.
 
13) Unwilling to abstain from alcohol for 48 hours prior to dosing at each of the dosing visits.
 
14) Participant has a positive alcohol test at Screening and/or Day -1 Visits.

--

Sponsor:	Investigational Product:	Developmental Phase:	IRAS ID Number:
Wave Life Sciences UK Limited	WVE-006	Phase 1	1008635

15) Any prescribed or recreational substance use (irrespective of legality) within 6 months prior to screening or unwilling to refrain from such use for the duration of the study.
 
16) Positive drug screen at Screening and/or Day -1 Visits.
 
17) Positive cotinine test at Screening and/or Day -1 Visits.
 
18) Use of prescription or non-prescription medications, including vitamin, dietary, and herbal supplements (including St John's Wort) within 7 days or 5 half-lives (whichever is longer) prior to the first dose of study treatment unless, in the opinion of the Investigator and Sponsor, the medication will not interfere with interpretation of study assessments. Contraception and hormone replacement therapy (HRT) are permitted. If needed, over-the-counter (OTC) medications such as paracetamol/acetaminophen may be used acutely.
 
19) History of major surgery in the 3 months prior to Screening Visit and/or planned surgery for the duration of the study.
 
20) Sustained hypertension defined as at least 2 repeated measurements at least 15 minutes apart of systolic pressure exceeding 130 mm Hg and/or diastolic pressure exceeding 80 mm Hg at Screening and/or Day -1 Visits.
 
21) Supine pulse rate <45 beats per minute (bpm) or >100 bpm at Screening and/or Day -1 Visits.
 
22) One or more of the following abnormal ECG findings at Screening and/or Day -1 Visits:
 
 Second- or third-degree atrioventricular block QRS >120 msec QTcF >450 msec for males or >470 msec for females PR interval >200 msec Any rhythm other than sinus rhythm that is considered clinically significant by the Investigator. 
23) History of risk factors for Torsade de Pointes including unexplained syncope, known long QT syndrome, heart failure, myocardial infarction, angina, or clinically significant abnormal laboratory assessments including hypokalemia, hypercalcemia, or hypomagnesemia.
 
24) Family history of long QT syndrome or Brugada syndrome.
 
25) Donation of blood or blood products in excess of 500 mL within 12 weeks prior to Screening Visit and/or unwilling to refrain from blood donation for the duration of the study.
 
26) Participant has any medical or social condition which in the opinion of the Investigator, would make the participant unsuitable for participation in the study, for study treatment, or could interfere with the assessments of safety or PK, or completion of the study.
 
27) Participant has received an investigational agent within 3 months or 5 half-lives (if known), or twice the duration of biological effect (if known), whichever is longer, before Screening, or who is in follow-up of another clinical study of an investigational agent at the time of the Screening Visit.
 
28) Exposure to more than 4 new chemical entities within 12 months prior to the Day 1 Visit.
 
29) Prior treatment with any oligonucleotide or small interfering RNA within 12 months prior to the Day 1 Visit.
 
30) Participant is directly or indirectly involved in the conduct and administration of this trial as an Investigator, sub-investigator, trial coordinator, or other trial staff member, or the participant is a first-degree family member, significant other, or relative residing with one of the above persons involved directly or indirectly in the trial.
			

Blinding: The roles indicated below will not be made aware of the treatment group assignment during the study:
 
 Participants 			

Sponsor: Wave Life Sciences UK Limited	Investigational Product: WVE-006	Developmental Phase: Phase 1	IRAS ID Number: 1008635

• Trial staff members (excluding pharmacy staff)• Investigator• DEC• Sponsor, with certain documented exceptions as per DEC Charter			
Data Monitoring/Other Committee: Because the Investigator is part of DEC and must remain blinded for long term safety evaluation, an independent unblinded DMC will review available data on PK and safety prior to dose escalation at each cohort.			
Statistical Methods: 
The sample size was not calculated on the basis of statistical hypothesis testing; however, the number of participants is considered sufficient for a Phase 1 assessment of safety, tolerability, and PK.
 
Treatment-emergent AEs overall and assessed as related to study drug or to study procedures, and treatment emergent SAEs, will be summarized for each dose group based on MedDRA coding of verbatim terms reported by Investigators. These summaries will be presented separately for Period 1 and Period 2.
 
Pharmacokinetic parameters for WVE-006 will be calculated using non-compartmental methods. PK parameters will be summarized by treatment using descriptive statistics: n, arithmetic mean, median, standard deviation (SD), minimum, maximum, and percent coefficient of variation (CV%); in addition, the geometric mean and geometric CV% will be reported for C_{max} and AUCs.
			

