4 STUDY DESIGN

4.1 Overall Study Design

This is a double-blind, placebo-controlled, single ascending dose (SAD) and multidose Phase 1 study to assess the safety, tolerability, and PK of WVE-006 in healthy participants. Participants will be randomized to WVE-006 or placebo.

Period 1 will evaluate single ascending doses of WVE-006 in up to five cohorts of up to 8 healthy participants each (3:1 active:placebo). An additional cohort (Cohort 6) may be included to evaluate concentration-QTc. Participants may be on-study for up to 12 weeks. A sentinel strategy will be employed for the first 2 participants (1 active:1 placebo) of every new dose level during the SAD portion (Period 1) and in the multiple dose portion (Period 2) of the study, with a 48-hour observation period to assess for acute safety events. The Dose Escalation Committee (DEC) and the DMC will review available data through Day 8 that will include key PK parameters and safety for each dose cohort, as well as previously accumulated safety data and available PK data, to recommend subsequent dose escalation. Additional details are provided in [Section 4.1.2](#).

Dose Escalation Stopping Criteria (Period 1):

Dose escalation will be paused until further evaluation by the DMC if any of the following criteria are met. If it is confirmed that a stopping criterion was met, no further dosing will take place until after submission and approval of a substantial amendment if the DMC recommends the trial can continue.

- One or more at least possibly related Common Terminology Criteria for Adverse Events (CTCAE) Grade ≥ 3 TEAE or CTCAE grade ≥ 3 laboratory abnormality in a single cohort.
 - All grade 3 toxicities for vital signs must be confirmed with a repeat measurement obtained within 1 hour.
 - All grade 3 toxicities for laboratory parameters must be confirmed with a repeat measurement obtained within 24 hours.
- Two or more at least possibly related CTCAE grade ≥ 2 TEAEs or CTCAE Grade ≥ 2 laboratory abnormalities in a single cohort.
 - All grade 2 toxicities for vital signs must be confirmed with a repeat measurement obtained within 1 hour.
 - All grade 2 toxicities for laboratory parameters must be confirmed with a repeat measurement obtained within 24 hours.
- Any at least possibly related SAE in a single cohort.

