In Period 2, a single cohort of up to 8 healthy participants including up to 6 WVE-006 and 2 placebo treated participants (3:1 active:placebo) will receive multiple doses of WVE-006. Participants may be on-study for up to 16 weeks. The DEC and DMC will review available

safety and PK data from Period 1 to select the maximum tolerated dose level (MTD) or other selected dose achieved if MTD was not reached. Additional information about treatment is provided in [Section 4.1.2](#). Individual treatment stopping criteria for participants in Period 2 are in [Section 7.1.1](#).

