4.1.2 Treatment

Period 1: Single Ascending Dose

Period 1 will evaluate single ascending doses of WVE-006 in up to five cohorts of up to 8 healthy participants each. Each cohort will include up to 6 WVE-006-treated and 2 placebo-treated participants (3:1 active:placebo). Participants will receive a single SC dose of WVE-006 or placebo on Day 1.

CCI

A sentinel strategy will be employed for the first 2 participants (1 active, 1 placebo) of every new dose level during the SAD portion of the study. The sentinel participants will be dosed and monitored in the clinic for 48 hours to identify any potential acute safety events. If neither of these sentinel participants experiences stopping criteria and if there are no other safety concerns during this 48-hour period, the remaining 6 participants will be randomized in a blinded fashion to active study drug (n=5) or placebo (n=1) and may be dosed on the same day. These participants will be observed in clinic for 48 hours after administration of study drug. Participants will attend weekly clinic visits on Weeks 0 through 12 to be followed for safety, tolerability, and PK assessments through Day 85 per the SoA.

If Period 1 Dose Escalation Stopping Criteria (see [Section 4.1](#)) are met at any point, dosing will be paused until further review and confirmation by the DMC. No further dosing will take place until after submission and approval of a substantial amendment if the DMC recommends the trial can continue.

Period 2: Multiple Doses

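### After the 48-hour sentinel check at dose 1, the protocol states no Period 2 event that pauses dosing for the other participants or requires DMC review

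*Combined protocol and SAP*

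**What the plan says.** The synopsis and Section 4.1 set cohort-level criteria under a heading that begins "Dose Escalation Stopping Criteria (Period 1". As the synopsis words them, they are: one participant with an at least possibly related Grade 3 or higher TEAE, or a Grade 3 or higher laboratory abnormality; two participants with such findings at Grade 2 or higher; or one with a related SAE. Any of these pauses escalation until the DMC has evaluated it. If the criterion is confirmed, dosing stays stopped until a substantial amendment is approved. Section 4.1.2, in its Period 1 part, says that if these criteria "are met at any point, dosing will be paused until further review and confirmation by the DMC".

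For Period 2, Section 4.1 offers a pointer: "Individual treatment stopping criteria for participants in Period 2 are in" Section 7.1.1. That section and the synopsis read: "Dosing will be paused or discontinued (per Investigator judgment) for an individual participant at any time in the study if" there is a related severe or serious event, clinically significant hypersensitivity, or a medical condition that the Investigator thinks makes further dosing unsafe. The synopsis adds that, on the Investigator's judgment after consulting the Sponsor, "the participant may be allowed to resume participation in the study if/when the event has resolved".

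The Period 2 sentinel rule releases the remaining 6 participants "If neither of these sentinel participants experiences stopping criteria and if there are no other safety concerns during this 48-hour period". On committee timing, the synopsis states that "an independent unblinded DMC will review available data on PK and safety prior to dose escalation at each cohort".

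**The concern.** Every Period 2 participant who starts treatment has two further doses to come, so an event in one participant bears directly on whether the others should be dosed again. In Period 1 each participant is dosed once, and the cohort rule mainly protects people not yet dosed and higher-dose cohorts. The protocol fixes a collective response in advance for Period 1 and none for Period 2.

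Without a rule, doses 2 and 3 for the others rest on discretion, held largely by blinded parties: the Investigator, the DEC, and the Sponsor with documented exceptions. The unblinded DMC is best placed to see whether a signal is on active drug. Section 2.3.3 relies on its systematic review of safety data as one of the two measures that minimise risk, yet no stated Period 2 event brings it in. The participants are healthy volunteers who, by Section 2.3.2, can expect no direct benefit.

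**Working it through.** The protocol gives no figure to reproduce here; Section 9.1 says the sample size does not rest on hypothesis testing. The check is mainly a comparison of text.

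**1. Same event, two periods**

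| Event | Period 1 | Period 2, after sentinel clearance |
|---|---|---|
| Related SAE | Pause, DMC evaluation, amendment if confirmed | Affected participant paused or discontinued; nothing stated for the others or the DMC |
| Related Grade ≥3 TEAE | Same | Same as the row above (Table 12 equates severe with Grade 3) |
| Grade ≥3 laboratory abnormality | Same, after a repeat within 24 hours | Not named; counts only if handled as a related severe or serious event, or if judged to endanger the participant |
| Two participants with related Grade ≥2 findings | Same, after a repeat (vital signs 1 hour, laboratory 24 hours) | Not named |

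**2. Provisions that could hold the Period 2 cohort**

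- Sentinel gate: covers 48 hours after the first dose only, and does not say which stopping criteria it means.
- Section 4.1.2 pause: tied to Period 1 criteria. A Period 1 criterion met late could halt Period 2 dosing, but this does not respond to a Period 2 event.
- Section 6.7: the DMC may reduce the remaining Period 2 doses. This is a reduction, not a pause, with no stated trigger.
- Section 10.1.5.1: the DMC oversees overall safety; report content and meeting frequency are left to its charter.
- Sections 7 and 10.1.9: the Sponsor may stop participation or terminate the study, at its discretion.

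Stated Period 2 events that, after sentinel clearance, pause dosing for the others or oblige DMC review: none.

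**3. Doses left scheduled for the others**

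Inputs (synopsis, Period 2): 6 active, 2 placebo, 3 doses. Assumptions: full enrolment, sentinels cleared, all 8 at the same dose number, one active participant affected, nobody uses discretion. With r doses remaining, the others have (6 − 1) × r active doses and (8 − 1) × r blinded injections.

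- After dose 1, r = 2: 5 × 2 = 10 active; 7 × 2 = 14 blinded.
- After dose 2, r = 1: 5 active; 7 blinded.
- After dose 3, r = 0: none.

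**4. Time available for a DMC review**

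Table 5 gives ±3 days for the Day 8, 15, 21 and 29 visits. The last in-window days for doses 2 and 3 are 15 + 3 = Day 18 and 29 + 3 = Day 32.

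- Found at the nominal visit: 18 − 8 = 10 days; 32 − 21 = 11 days.
- Found at the end of the visit window (Day 11 or Day 24): 18 − 11 = 7 days; 32 − 24 = 8 days.

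**5. How often a one-participant rule would fire**

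This bears on the cost of the fix, not on the gap. The documents give no event rates. Assume independent per-participant probabilities p of a related Grade ≥3 event in the 6 active participants: 1 − (1 − p)^6 is 0.11 at p = 2%, 0.27 at 5% and 0.47 at 10%. Placebo participants judged related under the blind would add to this.

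**The case against.** The best defence is that much already protects Period 2. The dose is chosen from Period 1 with a data requirement: "At least 4 weeks of safety data for the proposed dose and all available data from the study must be available from Period 1". It is the level below any that met a stopping rule, a well-tolerated top dose, or something lower, and Section 4.3 caps exposure at that seen at the NOAEL. At most 6 people receive active drug. SAEs reach the Sponsor within 24 hours and go on to ethics committees and, as required locally, regulators. The Investigator may unblind to treat an adverse event. Period 1 triggers also depend on a blinded Investigator's view of relatedness. A power to reduce the dose mid-period presupposes that the DMC sees Period 2 data, and its charter may contain a trigger. All of this stands and lowers the stakes. None of it is a stated Period 2 event that holds the other participants' doses.

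Three stronger readings are tempting and not supported:

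- A reader might infer that the Investigator could leave an affected participant on treatment. The wording says dosing will be paused or discontinued; the natural reading is that action is mandatory after a related severe or serious event, and judgment selects which. The gap concerns the others.
- A reader might infer that nobody could stop Period 2. The DMC, the Sponsor and the Investigator could act; what is missing is an event that obliges it.
- A reader might infer that all three Period 1 rules should carry over unchanged. The documents give no basis for setting the Grade 2 threshold under repeat dosing. Section 10.6 grades injection-site reactions on a separate scale, where erythema of 5.1–10 cm is Grade 2, so two such reactions could halt the cohort unless the rule says whether they count.

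**Conclusion.** The point holds in limited form. After the dose-1 sentinel gate, the protocol states no Period 2 event that pauses dosing for the remaining participants or requires DMC review, and resumption by an affected participant is settled between Investigator and Sponsor. Under the stated assumptions, up to 10 active doses (14 blinded injections) for the others stay scheduled after one related SAE or Grade 3 event following dose 1. That describes what the schedule permits; it does not predict harm or what the investigators would do.

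The conclusion rests on the protocol text alone. The visible Period 2 stopping text shows no redaction, but the DMC and DEC charters are not available. If the DMC charter already holds a trigger, the gap shrinks to a missing cross-reference. The change should be made: it is a cheap safeguard for healthy volunteers and uses a committee that already exists.

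**What to change.** In the synopsis and Sections 4.1, 4.1.2 and 7.1.1, state that all Period 2 dosing pauses pending unblinded DMC review if any Period 2 participant has an at least possibly related SAE, Grade 3 or higher TEAE, or Grade 3 or higher laboratory abnormality. Keep the Period 1 confirmation rules: vital signs repeated within 1 hour, laboratory values within 24 hours. In addition:

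- Make resumption after such an event depend on the DMC outcome, and say whether a substantial amendment is also needed.
- Have the Period 2 sentinel gate refer to this list.
- Align Section 6.7 (dose modification) and Section 7.2 (restart after a skipped dose).
- Leave any Grade 2 trigger to the sponsor and DMC. If adopted, count by participant as in the synopsis (Section 4.1 counts events), apply the same confirmation rules, and say whether injection-site reactions count.
- If the DMC charter already contains a trigger, cite it instead.

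The cost is protocol wording submitted as an amendment under Section 10.5.1, plus alignment of the two charters. No extra participants, visits or samples are needed. The downside is that a DMC review longer than 10 to 11 days from a nominal visit, or about 7 to 8 days from a late one, pushes a dose out of window and affects last-dose PK. If a substantial amendment is required before restarting, the remaining doses and the multiple-dose PK would probably be lost; the sponsor should weigh that explicitly.
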